Dry anal and cervicovaginal specimens will be processed and tested using the Atila Ampfire HPV genotyping. Upon arrival, the oral rinse specimen containers will be stored at 4°C refrigerators for processing the next working lab day. Dry brushes and associated labels will be stored in a box in the freezer at -20°C for processing the next working lab day. After testing, residual specimens will be aliquoted and stored frozen at -20°C for further testing.

[figure not shown]
HPV genotyping will be conducted within 2 months of collection to allow ample time to schedule the 6-12 month follow up visit for women who test HPV positive for any HPV type at any tissue site.

VI.F.2. Follow-Up Visit of the HPV-Positive Cohort

Participants who test positive for any of the 17 HPV types on their cervicovaginal, oral, and/or anal specimen collected at baseline will be scheduled for a 6-12 month follow-up visit with a window of 5-15 months after their baseline visit; participants who test negative on all three specimens will exit the study. Objectives of the follow-up visit are to 1) measure 6-12 month HPV persistence, an accepted primary endpoint in prophylactic HPV vaccine trials (89), and 2) ensure the safety of the participants. As outlined in **Figure 3**, at the follow-up visit, the participant's eligibility status will be confirmed. Participants will provide a urine sample for pregnancy testing to confirm they are not pregnant. Counseling will be provided pre and post testing as needed. Participants unknown to be living with HIV will have a rapid HIV test with pre- and post-HIV-testing counseling following the National Rapid HIV Diagnostic Testing Protocol. Any participant who tests positive will be referred to the health center's HIV clinic for

HIV management following the Ministry of Health's HIV management guidelines. Only specimens from those anatomic sites that were HPV positive at baseline will be collected utilizing the same protocol as at enrollment. A study staff will transport the oral saline rinse and dry swabs to the study lab to be stored until study testing for 17 HPV genotypes; the follow-up cervicovaginal and anal specimens will be tested within one month to ensure timely follow-up of high-risk individuals who need diagnostic services (colposcopy and/or anoscopy).

Figure 3. Activities at follow-up visit

VI.G. Study Test Results and Clinical Management

VI.G.1. Management of Persistent Cervicovaginal HPV

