There are no management guidelines or evidence-based intervention for type-specific persistent HPV. Therefore, participants will not receive any clinical intervention for type-specific persistent oral HPV.

VI.G.4. Study Exit

Other participants, including WLWH and/or those with persistent low-risk HPV6- or HPV11 infection, will exit the study.

VI.H. Biospecimen Processing, Storage, and Shipment

The study lab will process, store and test for HPV in oral specimens in saline solution, dry samples, blood samples and FFPE tissue specimens. All specimens will be tested for individual 17 HPV types using the AmpFire HPV genotyping test.

In preparation for testing, oral specimens will be aliquoted, the dry sample will be rinsed into a vial with lysis buffer and FFPE tissue specimens will be suspended in lysis buffer. Specimens will be processed according to manufacturer's instructions. All residual lysed specimens will be stored at the study lab at -80°C for later testing. Select samples will be sent to study collaborators' laboratory for microbiome testing. Additional microbiome testing will be conducted at the study lab.

Whole blood specimens will be processed to obtain aliquots of plasma. Following the protocol established by the Frederick National Laboratory of Cancer Research (FNLCR) HPV Serology Laboratory, select plasma specimens will be sent to FNLCR for testing and others will be tested at the study lab (**Section V.I.2**). After ELISA testing, residual plasma will also be stored at the study lab for later testing.

A biospecimen bank containing residual material from samples collected will be established at the study lab for subsequent methodologic and etiologic research.

VI.I. Laboratory Testing

VI.I.1. AmpFire HPV Testing

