All histopathology slides will be scanned at the study lab and reviewed by two local pathologists and the Einstein study pathologist (105). If the diagnoses are concordant, no further review of the case will be performed. If the diagnosis is discordant and at least one pathologist diagnoses CIN2+, the biopsy slide will be subjected to a joint review and consensus diagnosis. For Negative/cervical intraepithelial neoplasia grade 1 pairs of diagnoses, which does not influence our analyses or the care of the participants, there will be no joint review.

VII. STATISTICAL SECTION

VII.A. Specific Aim 1

To measure population effectiveness of prophylactic HPV vaccine in reducing cervicovaginal, anal, and/or oral prevalent and persistent infections by HPV6/11/16/18.

VII.A.1. Analyses.

We will calculate the point prevalence and the prevalence of persisting infection by individual HPV-type specific infections, with binomial 95% confidence intervals (95% CI), for each anatomic and for the woman (all anatomic sites) for Gardasil®-vaccinated WLWH, Gardasil®-vaccinated HIV[-] women, unvaccinated WLWH and unvaccinated HIV[-] women. We likewise will calculate the point prevalence and the prevalence of persisting infection with 95%CI for all

HPV types in aggregate and in sub-groups of HPV types according to the protection afforded by Gardasil®: Gardasil®-targeted types (HPV6, 11, 16, and 18), Gardasil®-untargeted types for which there might be cross-protection (HPV31, 33, and 45) (40, 106, 107), and Gardasil®-untargeted HPV types for which there is little or no evidence of cross-protection (HPV35, 39, 51, 52, 53, 56, 58, 59, 66, and 68). Results will be stratified by age and number of doses (3 vs. 2) as well as other factors possibly associated with HPV prevalence. Differences in the prevalence of these HPV type sub-groups (targeted, possible cross-protection, and untargeted) between the four study groups of women will be tested using Fisher's exact or Pearson chi-square test. Differences in the prevalence of these HPV type subgroups by age, number of doses (3 vs. 2), and other factors within the group, will be tested for statistical significance ($p<0.05$) using a Fisher's exact or Pearson chi-square test.

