Notably, the study groups of participants are fundamentally different populations (vs. a randomized control trial that would recruit from the same population and, as result of randomization, enroll similar, representative populations in each arm). Specifically, there are known differences in age (and therefore possible differences sexual behaviors) between Gardasil®-vaccinated vs. -unvaccinated WLWH, and possible differences in sexual behaviors between Gardasil®-vaccinated WLWH vs. HIV[-] women (since HIV infection predominately is sexually transmitted in this population). Therefore, we will use a relative measure of effectiveness to account for the differences in age and possible differences in exposure to HPV. We will use logistic regression to calculate the odds ratio (OR) of the point prevalence and the prevalence of persisting HPV infections of Gardasil®-targeted HPV types, individually (HPV6, 11, 16, or 18) and in aggregate (HPV6, 11, 16, and 18), vs. untargeted HPV genotypes for which there is no evidence of cross-protection, for each anatomic site individually (cervix, anus, OR oral cavity) and combined (cervix, anus, AND oral cavity). That is, we will compare the ratio between study groups of participants as follows:

$\frac{N_{HPV6/11/16/18}}{N_{HPV35/39/51/52/53/56/58/59/66/68}}$ [vaccinated WLWH] (Group 1)
 $\frac{N_{HPV6/11/16/18}}{N_{HPV35/39/51/52/53/56/58/59/66/68}}$ [unvaccinated WLWH] (Group 2)
 or

$\frac{N_{HPV6/11/16/18}}{N_{HPV35/39/51/52/53/56/58/59/66/68}}$ [vaccinated WLWH] (Group 1)
 $\frac{N_{HPV6/11/16/18}}{N_{HPV35/39/51/52/53/56/58/59/66/68}}$ [vaccinated HIV[-] women] (Group 3)

or

$\frac{N_{HPV6/11/16/18}}{N_{HPV35/39/51/52/53/56/58/59/66/68}}$ [vaccinated HIV[-] women] (Group 3)
 $\frac{N_{HPV6/11/16/18}}{N_{HPV35/39/51/52/53/56/58/59/66/68}}$ [unvaccinated HIV[-] women] (Group 4)

This will allow us to account for differences in HPV exposure, prevalence, and persistence due to differences in age (n.b., prevalence equals incidence * duration; prevalent infections at older ages tend to be more persistent ((108)) and sexual behaviors between groups. Additional logistic regression models may be used to adjust specifically on other factors, including age, number of doses, and sexual behaviors, to account for population differences between study groups.

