Similarly, exploratory analyses will compare the effectiveness of HPV vaccination for cross-protection types and endpoints of cumulative detection of Gardasil®-targeted HPV types-associated CIN2+ and/or anal intraepithelial neoplasia grade 2 or more severe (AIN2+) (vs. untargeted HPV type-associated CIN2+ and/or AIN2+) between study groups.

For participants in the existing IeDEA database we will extract HIV specific variables. For those who we cannot match to the IeDEA database, will extract HIV specific variables from medical records.

In another exploratory analysis, among WLWH, the presumed route of HIV acquisition (either maternal to child or behavioral) will be compared with HPV positivity and, among HPV-positive women, HPV viral load.

VII.A.2. Sample Size/Power for Gardasil®-vaccinated vs. unvaccinated WLWH.

For this analysis, we will make the following assumptions: 1) at least 30% prevalence of HPV infection (of any anatomic site) at baseline, 25% of which will be Gardasil®-target HPV types and 55% will be untargeted HPV types, 2) a 10% loss to follow-up (LTFU) in at follow up visit, and 3) at least 70% of HPV infections persist for 6-12 months. We justify an HPV prevalence of at least 30% based on 30% prevalence of high-risk HPV infection of the cervix in 30-year-old WLWH from our previous U54 study (109). We expect that the HPV prevalence may be higher since the prevalence of HPV, like that of other sexually transmitted infections, tends to peak about 5 years after the median age of sexual initiation in a population. However, we conservatively used 30% to ensure adequate statistical power. We justify our assumption of a maximum of 10% follow-up, given our experience working in Rwanda over the last ~20 years. We justify 70% of prevalent HPV infections persisting for 6-12 months, given that 36-50% of prevalent HPV infections persist 6-months in HIV[-] women (109, 110) and WLWH have an impaired immunity to HPV (8, 9).

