Sample size calculation relates to the relative effectiveness measure as discussed. Under above assumptions, a sample size of 757 vaccinated and 757 unvaccinated WLWH will provide $\geq 80\%$ power ($p=0.05$) to detect an OR of ≤ 0.5 for 6-12 month persistent HPV6/11/16/18 infections, relative to HPV35/39/51/52/53/56/58/59/66/68 (but not HPV31/33/45 because of possible cross protection), in Gardasil®-vaccinated vs. -unvaccinated WLWH. Consequently, because there will be more participants with a prevalent infection than 6-12 month persistent HPV infection (because there are no losses to follow-up or HPV viral clearance for which to account), there will

be $\geq 80\%$ power ($p=0.05$) to detect a OR of ≤ 0.75 in point prevalence of HPV6/11/16/18 infection relative to HPV35/39/51/52/53/56/58/59/66/68, in Gardasil®-vaccinated vs. - unvaccinated WLWH.

VII.B. Specific Aim 2

To quantify, and examine the determinants of, long-term antibody responses to, HPV vaccination.

VII.B.1. Analyses.

Geometric mean titers (GMT) and seropositivity (seroconversion) will be compared between 1) HPV-vaccinated WLWH and HPV-vaccinated HIV[-] women, overall and stratified on the number of vaccine doses, 2) HPV-vaccinated and unvaccinated WLWH, overall and by the number of doses received by the HPV-vaccinated WLWH, and 3) three vs. two doses for HPV-vaccinated WLWH and 4) HPV-vaccinated and unvaccinated HIV[-] women, overall and by the number of doses received by the HPV-vaccinated HIV[-] women.

Differences in GMT and seropositivity will be tested for statistical significance using the Mann-Whitney and Fisher's exact tests, respectively. ANOVA and logistic regression models will be used to adjust for/assess the association of other factors (e.g., age at vaccination, age at enrollment into the study, number of doses, HIV status [positive vs. negative and current antiretroviral therapy, CD4 counts, and HIV viral load] and history [e.g., CD4 nadir], and detection of HPV genotypes, etc.) with GMT and seropositivity, respectively.

Among vaccinated and unvaccinated HPV seropositive WLWH, the association between HPV antibody titer and presumed route of HIV acquisition (either maternal to child or behavioral) will be examined.

VII.B.2 Sample Size/Power to compare Gardasil®-vaccinated WLWH vs. Gardasil®-vaccinated HIV[-] women.

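### The Aim 1 targeted-versus-untargeted odds ratio has no defined record, co-infection rule or within-woman variance, so its interval, and partly its value, depend on an unstated coding

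*Combined protocol and SAP*

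**What the plan says.** - **Model (VII.A.1).** "We will use logistic regression to calculate the odds ratio (OR) of the point prevalence and the prevalence of persisting HPV infections", for the targeted types singly and in aggregate, against the ten types with no evidence of cross-protection. HPV31/33/45 are left out of that reference set. The model is to be run "for each anatomic site individually (cervix, anus, OR oral cavity) and combined (cervix, anus, AND oral cavity". It is displayed as N(targeted)/N(untargeted) in one group over the same ratio in another.
- **Purpose (VII.A.1).** "This will allow us to account for differences in HPV exposure, prevalence, and persistence due to differences in age", and to sexual behaviour. Models with further covariates are optional.
- **Hints at the unit.** Descriptive prevalence is given by type "for each anatomic and for the woman (all anatomic sites" included. The sample-size section (VII.A.2) starts from "at least 30% prevalence of HPV infection (of any anatomic site) at baseline" and divides infections into shares of 25% and 55%. It then justifies the prevalence power "because there will be more participants with a prevalent infection than 6-12 month persistent HPV infection".
- **Clustering.** GEE is named only for the exploratory persistence model (VII.C). Section IV accepts that infection is correlated across sites but gives no figure.
- **Inputs to the record.** At follow-up (VI.F.2), "Only specimens from those anatomic sites that were HPV positive at baseline will be collected". VI.H says "All specimens will be tested for individual 17 HPV types using the AmpFire HPV genotyping test". VI.I.1 describes one additional tube that detects HPV6 and HPV11 together, while VII.A.1 plans a model for each.

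**The concern.** This odds ratio is the plan's main effectiveness measure. N can be read in at least three ways: women, types per woman, or type-by-site detections. Each treats co-infected women and multi-site types differently, and an ordinary logistic model treats all its rows as independent. The same data can therefore give an interval that is too narrow, too wide or about right.

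The estimate moves as well. The ratio is meant to cancel exposure differences between groups of different age. If N counts women, the commoner untargeted category saturates first as exposure rises, so the cancellation is incomplete. With no vaccine effect, the OR then drifts below 1 if the unvaccinated group is more exposed, and above 1 if the vaccinated group is. A coding left open until the data are seen leaves this choice free on the main result.

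**Working it through.** The plan gives no figure for within-woman correlation, so there is none to reproduce. Its own counts set the starting point: 757 × 0.30 = 227.1 infections per group, of which × 0.25 = 56.8 are targeted and × 0.55 = 124.9 untargeted. With no vaccine effect and independent, exclusive units, the SE of the log OR is √[2(1/56.8 + 1/124.9)] = 0.226. The question is how far this formula holds under each coding.

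**1. Pooled type-by-site rows.** Let types occur independently, with a fraction q of them also found at a second site. Each type gives w = 1 or 2 rows, with E[w] = 1 + q and E[w²] = 1 + 3q. For n types, the plain variance is 1/[n(1 + q)] and the true variance is (1 + 3q)/[n(1 + q)²]. The SE ratio, plain to true, is √[(1 + q)/(1 + 3q)].
- q = 0: ratio 1.00, error 5.0%.
- q = 0.1: 0.92, error 7.1%.
- q = 0.3: 0.83, error 10.5%.
- q = 0.5: 0.775, error 12.9%.

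**2. Women counted in both categories.** Let a women be targeted-positive, b untargeted-positive and c both. The variance of log(a/b) is 1/a + 1/b − 2c/(ab), but the plain model uses 1/a + 1/b. If f is the share of positive women with both kinds, the SE ratio is √[(1 + f)/(1 − f)].
- f = 0.13: ratio 1.14, error 2.6%.
- f = 0.28: ratio 1.33, error 0.9%.

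This applies in single-site models as well as the combined one.

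**3. One record per type per woman.** If co-infection reflects only a shared level of exposure, then given the number of types a woman carries, each is targeted with the same probability. The plain interval is then about right.

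**4. Simulation.** From the plan: 757 women per group, 30% prevalence, the 25%/55% split, 70% persistence, 10% loss. Assumed: the remaining 20% of infections are HPV31/33/45; gamma frailty of shape 1.0 or 0.3 (13% or 28% of positive women with both kinds); second-site detection 0-50%; third-site detection 5% (0% in the 0% case); woman-level type-mix log-SD 0 or 0.8. There were 32 scenarios of 4,000 replicates, covering prevalent and persistent endpoints with no vaccine effect. Two-sided error at a nominal 5%:

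| Coding | Plain logistic | Clustered on woman |
|---|---|---|
| Pooled rows, second site 0 / 10 / 30 / 50% | 3.7-5.6 / 5.9-8.7 / 8.9-11.9 / 10.5-14.9% | 3.8-5.8% |
| Women in both categories | 0.6-3.6% | 3.8-5.8% |
| One record per type per woman | 3.0-5.7% | 3.8-5.8% |

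For women in both categories at a single site, the plain error was 3.1-4.0%, 2.0-4.4% and 1.0-3.6% at 10%, 20% and 30% site prevalence. Rarer sites were not tried.

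A separate simulation under other assumptions (6-33% of positive women with both kinds, anal detection 30-70%) gave SE ratios of 0.73-0.93, 1.03-1.41 and 0.95-1.19 for the three codings. The directions agree; the sizes differ.

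**5. Exposure, no vaccine effect.** Assume any-HPV prevalence p of 30% in vaccinated and 45% in unvaccinated women, with frailty shape 1.0. The mean number of types is μ = p/(1 − p) = 0.4286 and 0.8182. For a class with share s, the positive fraction is 1 − 1/(1 + sμ).
- Targeted (s = 0.25): 0.0968 and 0.1698.
- Untargeted (s = 0.55): 0.1908 and 0.3103.
- Either (s = 0.80): 0.2553 and 0.3956.
- OR, women in both categories: (0.0968/0.1908)/(0.1698/0.3103) = 0.93.
- OR, one row per woman (any targeted against untargeted only): (0.0968/0.1585)/(0.1698/0.2258) = 0.81, where 0.1585 = 0.2553 − 0.0968 and 0.2258 = 0.3956 − 0.1698.
- OR, types: 0.25μ/0.55μ is the same in both groups, so 1.

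Simulated over both frailty shapes and both endpoints, these three are 0.86-0.96, 0.62-0.86 and 0.99-1.05. At 35% against 30%, the first two are 0.96-1.00 and 0.87-0.98. With 45% in the vaccinated and 30% in the unvaccinated group, they are 1.04-1.17 and 1.16-1.61.

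**The case against.** The text is not wholly open. VII.A.1 begins with type-specific infections per site and per woman, goes on to infections of targeted types, and VII.A.2 splits infections. One record per type per woman is therefore the best-supported reading, and under it the variance part has little consequence. No section describes pooling type-by-site rows, and counting women in both categories errs on the safe side. All sizes rest on assumed co-infection and concordance. On exposure, VII.A.1 allows adjusted models, Section XI concedes that such techniques cannot fully control the bias, and near-cancellation for types itself assumes that exposure scales every type equally.

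Most of this stands, and it limits the point. It does not remove it: the woman-level wording belongs to descriptive prevalence, VII.A.2 also speaks of participants, and no co-infection rule appears anywhere.

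Three stronger readings are tempting, but the documents do not support them:
- **The planned intervals are too narrow.** That follows only for one coding, which the plan does not state.
- **This explains any shortfall from the 80% power in VII.A.2.** That is separate arithmetic on independent, exclusive units and is not counted here.
- **The HPV6/11 passages contradict each other.** One tube detecting both types need not mean one merged result. The text needs clarifying.

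**Conclusion.** The point holds as an omission that should be closed. VII.A.1 does not fix the record, the co-infection rule or the within-woman variance for its main effectiveness measure, and no other section does so.

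The directions are firm: too narrow for pooled type-by-site rows as concordance rises, too wide when co-infected women enter both categories, and about right to somewhat wide for one record per type per woman. Clustering on the participant brought error to about 4-6% for all three. Counting women also cancels exposure differences only partly; optional adjustment may reduce the residual bias but not remove it.

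The sizes are illustrative and are not bounds. The main gap is the definition of the record. Clustered variance is a nearly free safeguard, but it does not settle what is being estimated.

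**What to change.** Add to VII.A.1:

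> The model uses one record per type among HPV6/11/16/18 (targeted = 1) and HPV35/39/51/52/53/56/58/59/66/68 (targeted = 0), with study group as covariate; HPV31/33/45 are excluded. Prevalence models use types detected at baseline. Persistence models use only types that persisted, meaning the same type at the same site at both visits. Site-specific models use the types at that site; the combined model counts a type once per woman across sites. A woman with both targeted and untargeted types contributes a record for each. Models for a single targeted type drop records of the other targeted types. All models use GEE with independence working correlation and robust variance clustered on the participant.

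Also state, consistently in VI.H, VI.I.1 and VII.A.1, whether the HPV6/11 tube reports the two types separately. If it does not, use one combined targeted record and no separate HPV6 and HPV11 models.

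If the team means N to be women, say so, give the co-infection rule, keep the participant-clustered variance, and note that exposure is not fully cancelled.

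The cost is a few sentences and a standard software option, with no new data. The downside is that multiply infected women carry more weight and the estimand is fixed as types per woman, so the choice belongs to the team and should be made before the data are analysed.
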